**Non-Relapse Mortality:**

Defined as time interval from date of first dose of study drug to death from any cause among patients without active disease.

**Chronic GVHD Symptom Score:**

Patients will self-report symptoms and signs of cGVHD using the validated chronic GVHD Symptom Scale. Self-Reported symptom Scales will be obtained at baseline and weeks 3, 7, 9, 12 and 16.

**Steroid Use for Chronic GVHD:**

Patients will have their total daily dose of corticosteroids recorded at baseline, and at 3, 7, 9 12 and 16 (or 4 weeks after end of treatment) weeks of IL-2+ ECP therapy. In the case of alternate daily dosing of corticosteroids, the average daily dose will be recorded for study purposes.

**Immune Assessment:**

Patients will undergo testing for immunologic function, performed at baseline and at weeks 3, 7, 9, 12 and 16 (or 4 weeks after end of treatment). Testing will include: quantitative immune globulins; plasma banking; and storage of additional mononuclear cells.

**ECP Performance Parameters:** Clinical Response to therapy will be co-related with ECP performance parameters which will include median time spent on ECP machine, second versus third generation device ( Cellex vs XTS) and flow rates.

## 12.0 Data Reporting

---

### 12.1 Confidentiality and Storage of Records

This protocol uses Electronic Data Collection, and the data will be stored in encrypted, password protected, secure computers that meet all HIPAA requirements. When results of this study are reported in medical journals or at meetings, identification of those taking part will not be disclosed. Medical records of subjects will be securely maintained in the strictest confidence, according to current legal requirements. They will be made available for review, as required by the FDA, HHS, or other authorized users such as the NCI, under the guidelines established by the Federal Privacy Act and rules for the protection of human subjects.

#### 12.1.2 Subject Consent Form

At the time of registration, the original signed and dated Informed Consent form, HIPAA research authorization form, and the California Experimental Subject's Bill of Rights (for the medical record) and three copies (for the subject, the research record, and the Coordinating Center) must be available. All Institutional, NCI, Federal, and State of California requirements will be fulfilled.

#### 12.1.3 Data Collection Forms and Submission Schedule

All data will be collected on Medidata Rave®. Data will be stored in encrypted, password protected, secure computers that meet all HIPAA requirements.

Form	Submission Timeline
Eligibility Checklist	Complete prior to registration
On Study Forms	Within 10 business days of registration
Baseline Assessment Forms	Within 10 business days of registration
Treatment Forms	Within 10 business days of treatment administration
Adverse Event Report Forms	Within 5 business days, but only through day 60 (DLT period)
Response Assessment Forms	Within 10 business days of response assessment
Other assessment forms (e.g. concomitant meds, chemistry, hematology, neuro exam, physical exam)	Within 10 business days of the assessment
Off Treatment/Off Study Forms	Within 10 business days of completing treatment or being taken off study for any reason
Follow up/Survival Forms	Within 10 business days of the protocol defined follow up visit date or call

## 13.0 Statistical Considerations

---

### 13.1 Study Design, Sample Size, and Accrual Rate

This single center/single arm, phase II clinical trial is designed to evaluate the anti-cGVHD activity of extracorporeal photopheresis (ECP) when combined with low dose IL-2, in patients with steroid refractory cGVHD, as assessed by overall cGVHD response rate (CR+PR+SD). The primary endpoint overall response (CR+PR+SD) is based on the NIH cGVHD consensus criteria; calculated as the percent of evaluable patients that have confirmed CR/PR or SD

This study will implement a Simon, optimal, two-stage design to evaluate the anti-cGVHD activity of the ECP/IL-2 regimen. The trial is expected to enroll 24 patients e sample size is based on the desire to discriminate a promising response rate of 50% from a current response rate of 25%. The null hypothesis

that the true response rate is 25% will be tested against a one-sided alternative. In the first stage, 9 patients will be accrued. If there are 2 or fewer responses in these 9 patients, the study will be stopped. Otherwise, 15 additional patients will be accrued for a total of 24. The null hypothesis will be rejected if 10 or more responses are observed in 24 patients. This design yields a type I error rate of 0.05 and power of .80 when the true response rate is 50%. Currently, about 20-25 new patients are referred to ECP per year. We expect that 6 patients to be enrolled per year with the expected completion of accrual in 4 years.

**Evaluable for Response:** As part of the primary analysis, patients will be considered evaluable for response if they are eligible, have baseline disease assessments, and receive protocol treatment of any duration. All such patients will be evaluated for clinical response. Our primary outcome will be the clinical response rate measured in all patients who are enrolled and receive any amount of protocol therapy.

Patients who are consented for the study but withdraw for any reason (progression of GVHD, infectious complications, insurance denial etc) prior to initiation of protocol therapy will not be eligible for response evaluation.

**Evaluable for Toxicity:** Patients will be considered evaluable for toxicity if they receive any study drug.

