## Protocol Synopsis

---

Protocol Title:
A Phase II trial of extracorporeal photopheresis (ECP) plus low dose IL-2 for the treatment of steroid refractory chronic graft-versus-host disease (cGVHD)
Brief Protocol Title for the Lay Public (if applicable):
Immunotherapy with IL-2 and ECP for refractory chronic graft versus host disease
Study Phase:
Phase II, non-randomized single institution trial.
Participating Sites:
City of Hope National Medical Center
Rationale for this Study:
Impaired immune reconstitution due to alteration in the ratio of regulatory T cells (Tregs) and conventional T cells (Tcon) post hematopoietic cell transplant is responsible for clinical manifestations of chronic GVHD. We propose that the combination of ECP and IL-2 will have a synergistic effect on increasing the proportion of Tregs, leading to normalization of Treg: Tcon ratio. This should lead to improved overall response rates (CR, PR and stable disease) when IL-2 and ECP are used in combination, compared to historical controls when either modality is used alone.
Objectives:
Primary: To evaluate the anti-cGVHD activity of extracorporeal photopheresis (ECP) when combined with low dose IL-2, in patients with steroid refractory cGVHD, as assessed by overall cGVHD response rate (CR+PR+SD).
Secondary:

 
• Characterize and evaluate toxicities, including type, frequency, severity, attribution, time course and duration.
 
• Estimate overall and failure-free survival, non-relapse mortality (NRM) and relapse, through 1 year after initiation of treatment.
 
• Characterize the chronic GVHD Symptom Scale scores
 
• Determine ongoing prednisone use with IL-2 and ECP combination therapy.
 
• Assess the immunologic effects of low-dose daily SC IL-2 + ECP.
 
• Correlate clinical endpoints of response with ECP performance parameters.
 

Study Design:
Single-arm, single institution Phase II trial to estimate the activity of low dose IL-2 and ECP in patients with steroid refractory GVHD.
Endpoints:
Overall response rate to a 12-week course of subcutaneous low-dose daily IL-2 plus ECP in patients with steroid-refractory cGVHD. The primary endpoint of overall response is as defined in Section 11.0. Responses will be assessed at 3 weekly intervals while on IL-2 + ECP.
Sample Size:

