### 1.1 Primary Objective

To evaluate the anti-cGVHD activity of extracorporeal photopheresis (ECP) when combined with low dose IL-2, in patients with steroid refractory cGVHD, as assessed by overall cGVHD response rate (CR+PR+SD).

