### 11.1 Primary Endpoint

The primary activity endpoint is cGVHD response, based on the 2014 cGVHD NIH Consensus criteria. Confirmation of CR/PR or SD assessed by NIH Consensus criteria.

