##### **Overall Response:**

Improvement in measure at least one organ or site, without progression in measures at any other organ or site. The NIH global severity of chronic GVHD assessment criteria will be used to evaluate the response to therapeutic intervention in one or more involved organs. Of note, for global ratings and categorical scales, a 1-point change in a 3- or 7- point scale or a 2- to 3- change on a 0- to 10- point scale (0.5 SD change) would be considered clinically meaningful. Additionally, the hallmark for response to therapy for bronchiolitis obliterans syndrome (BOS) is stabilization of lung function with no further decrease in FEV1 during a 3-month period.

**Progressive Disease:** Organ progression: an absolute increase of at least 25% in the scale used to measure disease manifestations related to cGVHD. Of note, for global ratings and categorical scales, a 1-point change in a 3- or 7- point scale or a 2- to 3- change on a 0- to 10- point scale (0.5 SD change) would be considered clinically meaningful. Additionally, clinical worsening of cGVHD is not synonymous with progressive cGVHD per NIH criteria, as patients may experience worsening symptoms that do not meet objective NIH criteria for progression. If so, they still have the option of discontinuation of IL-2 and initiating additional immunosuppression for lack of IL-2 efficacy; at the judgment of the treatment physician.

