#### 13.2 Statistical Analysis Plan

Patient demographic and baseline characteristics, including age, gender, medical history, and prior cGVHD therapy, will be summarized using descriptive statistics. For continuous variables, descriptive

statistics (number [n], mean, standard deviation, standard error, median (range) will be provided. For categorical variables, patient counts and percentages will be provided.

The overall response rate (CR+PR) will be calculated as the percent of evaluable patients; exact 95% confidence intervals will be calculated for these estimates. Response rates will also be evaluated based on number and type of prior therapy(ies). Time to response, duration of response, and survival will be estimated using the product-limit method of Kaplan and Meier.

Observed toxicities will be summarized in terms of type (organ affected or laboratory determination), severity, time of onset, duration, probable association with the study treatment and reversibility or outcome. Baseline information (e.g. the extent/type of prior therapy) and demographic information will be presented as well to describe the patients treated in this study.

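### Section 13.1 tests CR+PR+SD, but section 13.2 gives the overall response rate and its only exact interval for CR+PR; separately, the 25% null has no cited source

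*Combined protocol and SAP*

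**What the plan says.** The primary objective in section 1.1 is anti-cGVHD activity "as assessed by overall cGVHD response rate (CR+PR+SD"), and the schema and synopsis agree. Section 13.1 repeats this ("The primary endpoint overall response (CR+PR+SD) is based on the NIH cGVHD consensus criteria") and says how the rate is obtained: "calculated as the percent of evaluable patients that have confirmed CR/PR or SD". The design is a Simon optimal two-stage test meant to "discriminate a promising response rate of 50% from a current response rate of 25" per cent, one-sided. Stage 1 has 9 patients and the trial stops at 2 or fewer responses. Otherwise 15 more are enrolled, and the null is rejected at 10 or more of 24.

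Section 13.2 then says: "The overall response rate (CR+PR) will be calculated as the percent of evaluable patients; exact 95% confidence intervals will be calculated for these estimates". It does not mention CR+PR+SD and does not label CR+PR as secondary.

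The synopsis sends the reader elsewhere for the definition: "The primary endpoint of overall response is as defined in Section 11.0". Section 11.1 includes SD ("Confirmation of CR/PR or SD assessed by NIH Consensus criteria"), but section 11.1.1 writes out CR, PR and progression only.

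The 25% appears in the synopsis and in 13.1 as the current response rate, without a citation. The synopsis and section 2.2 give the hypothesis as a better CR, PR and SD rate than either modality has achieved alone.

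**The concern.** Sections 13.1 and 13.2 share a term and a denominator but not a numerator. An analyst who follows 13.2 attaches the planned interval to a quantity that was not tested, and the tested quantity gets none. A report could then say that the null was rejected and, in the same paragraph, give an overall response rate equal to the null. Which rate to present as primary would be settled after the data are known.

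The second issue is what a rejection means. The test controls error at 25% only. If the rate without any added benefit is higher than that for an endpoint that counts SD, the rule can be met often without any gain from combining the treatments. Because the 25% has no source, a reader cannot judge how likely that is.

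**Working it through.** **Inputs (section 13.1).** n1 = 9, stop at 2 or fewer; n = 24, reject at 10 or more; p0 = 0.25, p1 = 0.50; nominal type I error 0.05 and power 0.80.

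**Step 1: reproduce the design.** With X1 ~ Bin(9, p) and X2 ~ Bin(15, p),

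P(reject | p) = Σ over x = 3 to 9 of P(X1 = x) · P(X2 ≥ 10 − x).

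- At p = 0.25, the terms for x = 3, 4, 5, 6 and 7 are 0.0132, 0.0173, 0.0122, 0.0047 and 0.0009, and the rest add about 0.0001. The total is 0.0485.
- At p = 0.50, the terms for x = 3 to 9 are 0.1142, 0.2090, 0.2315, 0.1612, 0.0701, 0.0176 and 0.0020. The total is 0.8055 after rounding.

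The probability of stopping at stage 1 under the null is 0.601, so the expected sample size is 9 + (1 − 0.601) × 15 = 15.0. A search over two-stage designs confirms 2/9 and 9/24 as the optimal design for 25% versus 50%. The stated 0.05 and 0.80 are correct as nominal limits.

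**Step 2: the two definitions on the same data.** The intervals are Clopper-Pearson for x of 24, the usual exact interval, with no adjustment for the interim look. The splits between CR/PR and SD are illustrative, and each assumes at least 3 responses (SD included) among the first 9 patients.

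| Outcome in 24 patients | CR+PR+SD (tested, 13.1) | Decision | CR+PR (reported, 13.2) |
|---|---|---|---|
| 6 CR/PR, 5 SD | 11/24 = 46%, CI 26% to 67% | reject | 6/24 = 25%, CI 10% to 47% |
| 7 CR/PR, 3 SD | 10/24 = 42%, CI 22% to 63% | reject | 7/24 = 29%, CI 13% to 51% |

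In the first row the reported rate equals the null value although the null was rejected.

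**Step 3: behaviour away from 25%.** The same formula gives:

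| True CR+PR+SD rate | P(reject) |
|---|---|
| 25% | 0.05 |
| 30% | 0.14 |
| 35% | 0.28 |
| 40% | 0.47 |
| 45% | 0.66 |
| 50% | 0.81 |

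**Step 4: can the documents supply the comparator rate?** They cannot.

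- For ECP, section 2.1.2 gives about 30% in its own summary, 22% + 34% = 56% in a retrospective cutaneous series, 61% (visceral) and 71% (cutaneous) in a prospective study, and 64% in each of two meta-analyses. It also gives a stricter week-12 composite of 8.3%. For lung, the two meta-analyses give 15% and 48%.
- For IL-2, the figure is 12/23 = 52% (CI 31% to 73%). Section 2.1.3 calls these major responses; section 2.1.4 calls the 52% PR plus SD.
- The denominator alone matters. Using the 28 patients evaluable for toxicity in that IL-2 trial, 12/28 = 43%, where P(reject) is 0.58; at 12/23 it is 0.85.

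None of these is a 12-week CR+PR+SD rate for one modality alone.

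**The case against.** **The primary rate is still planned.** Section 13.1 itself defines the CR+PR+SD percentage and fixes both Simon decisions, and 13.2 never calls CR+PR primary. This stands. A reader might infer that 13.2 replaces the primary estimate or changes the go/no-go decision, but the documents do not support that. In the example, 11/24 is produced as well as 6/24. What is missing is an interval for the tested rate and a label that separates the two.

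**Section 11 may settle SD.** A reader might infer that section 11.1.1 excludes SD, because its text under Overall Response asks for "Improvement in measure at least one organ or site, without progression in measures at any other organ or site". That text follows directly after the organ-level definition of PR, and CR has both an organ and an overall level, so it reads most naturally as the overall level of PR. SD can also be read as whatever is neither CR, PR nor progression, and the cited NIH criteria or the appendices, which are not in the text reviewed, may define it. So SD is not written out in 11.1.1, but it cannot be called undefined.

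**The 25% may be reasonable.** A reader might infer from the 52% and 64% figures that 25% is too low. The documents do not establish this. The Study Calendar section excludes oral and ocular sites from response, while one of the ECP meta-analyses quotes 72% for oral and 60% for ocular disease. Section 3.1.6 allows prior ECP and any number of prior lines. The denominator in 13.1 is everyone who receives any protocol therapy. Each of these could lower the comparable rate. The 7 in-house patients, all with PR or SD, are a small off-protocol series, described as single-agent IL-2 in section 2.1.3 and as the combination in section 2.1.4.

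**Every single-arm test controls error only at its null.** This is true. It is why the second point limits the stated conclusion and does not call for a redesign.

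**Conclusion.** The mismatch between 13.1 and 13.2 is literal and needs correction. As written, the tested primary endpoint has no planned confidence interval, and the term overall response rate has two numerators. The gap between the two reported rates is the number of SD patients divided by 24, which is 5/24 = 21 percentage points in the first example. The true number of SD patients is unknown. The sample-size arithmetic and the decision rule are sound.

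The secondary point is weaker. The 25% has no cited source, and no comparable single-modality rate can be derived from the documents. It follows that rejection supports a rate above 25% and does not by itself support the hypothesis of improvement over ECP or IL-2 alone. It does not follow that 25% is wrong.

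**What to change.** 1. Use one definition of overall response in sections 1.1, 11.1, 13.1 and 13.2, for both Simon decisions and for the primary rate with its exact 95% CI. The smallest change is to keep CR+PR+SD and name it in 13.2.
2. If SD counts, state its definition in 11.1.1, or point to the exact place in the NIH criteria or the appendix that gives it.
3. In 13.2, report CR+PR (with its CI) and SD as separately labelled rates, so that readers can see how much of the primary rate is stabilization.
4. If 25% is kept, give its source and add a sentence to 13.1: rejection shows only a rate above 25% and does not by itself show improvement over ECP or IL-2 alone. The hypothesis in the synopsis and section 2.2 can stay as a hypothesis.

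The cost is wording and a more modest stated conclusion, with no extra patients and no change to the boundaries. Re-sourcing both 25% and 50% for the chosen endpoint is an alternative to item 4, but it is a trade-off: it would change the boundaries if the rates change, and possibly the sample size.

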### **5.5 Criteria for Removal from Treatment**

- Subject withdraws consent
- Non-compliance
- Administrative reasons (insurance loss or no coverage of IL-2 or ECP by third party payors)
- Any Grade 4 non hematologic adverse event
- Life threatening anaphylactic reaction to IL-2
- Recurrent or non-resolving grade 3 toxic event
- Malignant relapse
- Clinical worsening of GVHD requiring the addition of a new immunosuppressive medication. A 50% increase in the corticosteroid dose will be considered evidence of worsening GVHD. Changes in other immunosuppressive medication doses to maintain a therapeutic level alone will not be criteria for removal from the trial.

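### Stable disease counts as success in the primary endpoint, but SD, confirmation, the scoring visit and failure events are not defined, so a patient switched for lack of efficacy can score as a responder

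*Combined protocol and SAP*

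**What the plan says.** - **What counts.** Sections 1.1 and 13.1 count CR, PR and SD as response. Section 13.1 describes the endpoint as "calculated as the percent of evaluable patients that have confirmed CR/PR or SD"; section 11.1 adds "Confirmation of CR/PR or SD assessed by NIH Consensus criteria". Neither gives an interval, a repeat assessment or an assessor for the confirmation.
- **When.** The Synopsis ties the endpoint to a 12-week course and says "Responses will be assessed at 3 weekly intervals while on IL-2 + ECP". Section 10.0 schedules NIH assessments at baseline and weeks 3, 7, 9, 12 and 16. No place names the visit that decides the endpoint, or says whether best response is meant.
- **Categories.** Section 11.1.1 defines CR, organ-level PR, an overall response (improvement somewhere and progression nowhere) and organ-level progression. It does not define SD. Section 5.3 also mentions a minor response, likewise undefined.
- **Switching.** Section 11.1.1 accepts that symptoms can worsen without meeting NIH progression, and says of such patients that "they still have the option of discontinuation of IL-2 and initiating additional immunosuppression for lack of IL-2 efficacy". Section 5.5 lists as a ground for removal from treatment: "Clinical worsening of GVHD requiring the addition of a new immunosuppressive medication". Neither section says how the patient scores in the primary endpoint.
- **Who is analysed.** Under section 13.1, every eligible patient with a baseline assessment who was treated, however briefly, is evaluable for response.
- **Decision rule.** The null hypothesis "that the true response rate is 25% will be tested against a one-sided alternative". Nine patients enter stage 1, and the trial stops at 2 or fewer responses. Otherwise 15 more enter, and 10 or more responses in 24 reject the null.

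**The concern.** In a single-arm trial the go/no-go decision is a count of patients labelled as responders, set against a fixed rate. Whatever loosens the label raises the rate that the endpoint would reach without any real activity, and the 5% error rate holds only if that rate is 25%.

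SD is the category most exposed to this. Entry requires two weeks on an unchanged steroid dose (section 3.1.4), and section 5.2.4 allows no taper for the first six weeks. Stability at an early visit on unchanged background treatment therefore says little about the new combination. If SD also takes in patients whose treatment was changed because it was not working, the count would credit the regimen with failures.

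The margins are small. At stage 1, one reclassified patient turns 2 of 9 (stop) into 3 of 9 (continue). At the end, two reclassified patients turn 8 of 24 into 10 of 24, a positive trial.

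**Working it through.** **Step 1: reproduce the plan's figures.** The inputs, all from section 13.1, are n1 = 9, stop at ≤ 2, n2 = 15, reject at ≥ 10 of 24, p0 = 0.25 and p1 = 0.50.

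Probability of stopping at stage 1, P(X1 ≤ 2):
- at p = 0.25: 0.75^9 + 9(0.25)(0.75^8) + 36(0.25²)(0.75^7) = 0.0751 + 0.2253 + 0.3003 = 0.6007;
- at p = 0.50: (1 + 9 + 36)/512 = 0.0898.

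Probability of rejecting the null: Σ over x1 = 3 to 9 of P(X1 = x1 | 9, p) × P(X2 ≥ 10 − x1 | 15, p).
- at p = 0.25: 0.0485;
- at p = 0.50: 0.8055.

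Section 13.1 claims: "This design yields a type I error rate of 0.05 and power of .80 when the true response rate is 50"%. Both figures reproduce. A search over two-stage designs also returns 2/9 and 10/24 as optimal, with expected size under the null 9 + 15 × (1 − 0.6007) = 14.99. The arithmetic is sound; the gap lies in what counts as a response.

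**Step 2: follow the switched patient through the text.**
1. The patient worsens, but not enough for NIH progression (11.1.1). The patient is not PD.
2. IL-2 is stopped and new immunosuppression is started for lack of efficacy (11.1.1). Section 5.5 takes the patient off treatment.
3. Section 13.1 keeps the patient in the denominator.
4. With neither CR nor PR and no PD, SD is the only one of the four categories left, and SD is a success.
5. No rule interrupts this. Section 11.2 names failure events for failure-free survival, but the primary endpoint has no counterpart.

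**Step 3: transient SD.** If any visit may supply the response, SD at week 3 followed by progression at week 7 could count. This needs an any-visit reading without a confirming assessment. Nothing in the text rules that reading out, but nothing prescribes it.

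**Step 4: size, for illustration only.** Assume a rate of 25% under a strict rule (fixed visit; progression or switch is failure), and let loose scoring add x percentage points. The documents do not give x. The formula in step 1 at p = 0.25 + x gives:

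| Added points | Extra patients in 24 (24 × x) | Rate scored | P(declare activity) |
|---|---|---|---|
| 0 | 0 | 25% | 4.8% |
| 5 | 1.2 | 30% | 13.7% |
| 10 | 2.4 | 35% | 28.4% |
| 15 | 3.6 | 40% | 47.1% |

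**The case against.** The strongest reply is that the plan is less empty than it looks. It requires confirmation, refers to a 12-week course, and defers to the NIH consensus criteria and to appendices that are not in the supplied text. A definition of SD or of overall progression may sit there. Section 13.2 even gives the overall response rate as CR+PR; if that governed, SD would not be a success at all.

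Much of this stands, and it rules out several stronger conclusions that a reader might draw:
- *That the 10-of-24 count will include treatment failures.* The text leaves this open; it does not prescribe it.
- *That SD at week 3 followed by progression at week 7 is a success.* On an ordinary reading of confirmation, the next visit would fail to confirm it.
- *That a mixed response scores as SD.* Section 11.1.1 bars overall response when another organ progresses, and its progression entry is organ progression. PD is the natural reading.
- *That a patient with no assessment after baseline could count as a success.* There is nothing to confirm, so that patient already cannot be a responder.
- *That the trial's type I error is 28% or 47%.* Those figures rest on assumed shifts, and also on 25% being the null under a strict rule, which the plan does not state.

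The reply does not reach the switched patient. Even if an appendix defines SD, the scoring visit, the meaning of confirmation and the handling of a treatment switch are choices for this trial and belong in sections 11 and 13. The CR+PR wording in 13.2 conflicts with the SD-inclusive objective and decision rule; it does not settle the matter.

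**Conclusion.** The point holds. The primary endpoint cannot be scored reproducibly from the supplied text, and the stated rules can place a treatment failure in a category that counts as success. The switch for lack of efficacy is well supported by sections 11.1.1, 5.5 and 13.1 read together. Transient SD is a weaker, possible route.

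The size is unknown, because the documents give no share of switched or transient SD. The figures of 13.7%, 28.4% and 47.1% show only how sensitive the rule is if 5, 10 or 15 points are added to a strict rate of 25%. The stated operating characteristics themselves are correct. The point should be settled before responses are counted, because otherwise the definition could be chosen with the results in view.

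**What to change.** These changes concern endpoint scoring only and alter no treatment rule.

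In sections 11.1 and 13.1:
- Fix the primary scoring visit. Week 12, the end of the planned course, is the natural choice; state what confirmation means at that visit.
- Define SD as not meeting CR, PR or PD.
- State that progression in any assessed organ is overall PD (section 10.0 leaves oral and ocular sites out of response).
- Count as non-responders patients who, before that visit, start new systemic immunosuppression for cGVHD, meet the plan's own worsening criterion in section 5.5, relapse, die, or have no assessment at that visit.
- Report best response as a secondary result.

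Reconcile with section 13.1 at the same time:
- section 13.2, which gives the response rate as CR+PR;
- section 5.2.4, which says progression during taper is not lack of efficacy, and so meets the PD rule head-on;
- section 6.1, which makes patients with an interruption of six weeks or more unevaluable unless improvement was documented, while 13.1 analyses any length of treatment.

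The cost is wording in these sections and an observed rate that is less favourable by an unknown amount. The sample size and decision rule need not change on this account. The fix does not show that 25% is the right null for an endpoint that includes SD; the aim to "discriminate a promising response rate of 50% from a current response rate of 25"% still needs support on that basis.

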### **4.1 Screening Procedures**

The following evaluations must be performed within four weeks prior to IL-2 +ECP treatment for all patients on protocol:

- Medical history and documentation of rationale for enrollment on IL-2 + ECP therapy on protocol.
- Physical examination, documentation of vital signs and KPS.
- Chronic GVHD assessment based on NIH consensus criteria – see Appendix C.
- Baseline lab work including CBC with differential, CMP and TSH/Vitamin D screen.
- Serum samples and mononuclear cells to be collected for immune assessment.
- Pregnancy test for women of childbearing age.
- Pulmonary function tests for patients with pulmonary manifestations of cGVHD.
- Dermatologic assessment for patients with cutaneous cGVHD.
- Flexion assessment of affected joints for individuals with contractures or musculoskeletal involvement secondary to cGVHD.

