### **4.3 Registration Requirements/Process**

Following informed consent, the patient will be registered through the Clinical Trials Office (CTO) prior to the initiation of therapy. Any participant not registered to the protocol before treatment begins will be considered ineligible and registration will be denied. A member of the study team will confirm eligibility criteria and complete the protocol-specific eligibility checklist.

[figure not shown]
Following registration, participants may begin protocol treatment. Issues that would cause treatment delays should be discussed with the Principal Investigator. If a participant does not receive protocol therapy following registration, notify the CTO of participant status changes as soon as possible.

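### Section 13.1 defines the primary response denominator in two incompatible ways, so a treated patient later found ineligible, or lacking a baseline assessment, is excluded by one sentence and counted by the other.

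*Combined protocol and SAP*

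**What the plan says.** The paragraph on evaluability for response in section 13.1 opens, for the primary analysis, with three conditions: "patients will be considered evaluable for response if they are eligible, have baseline disease assessments, and receive protocol treatment of any duration". It then says: "Our primary outcome will be the clinical response rate measured in all patients who are enrolled and receive any amount of protocol therapy". The second sentence drops the conditions on eligibility and baseline assessment.

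The calculations elsewhere refer back to evaluability. Section 13.1 describes the primary endpoint as "calculated as the percent of evaluable patients that have confirmed CR/PR or SD", and section 13.2 says "The overall response rate (CR+PR) will be calculated as the percent of evaluable patients". (The two also differ on whether stable disease counts, which is a separate matter.)

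The only other exclusion in 13.1 concerns patients who consent but withdraw: those who do so "prior to initiation of protocol therapy will not be eligible for response evaluation". It does not reach anyone who has been treated.

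Three provisions bear on how often the conflict could arise:
- Section 4.3: "A member of the study team will confirm eligibility criteria and complete the protocol-specific eligibility checklist".
- Section 4.1: "The following evaluations must be performed within four weeks prior to IL-2 +ECP treatment for all patients on protocol". The list that follows includes the chronic GVHD assessment.
- Section 12.1.3 requires the eligibility checklist before registration and the baseline forms within 10 business days after it.

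**The concern.** Both sentences govern the same rate, and they disagree about a treated patient who turns out not to have met a criterion or who has no baseline assessment. No section says how to count such a patient.

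The trial has 24 patients and decides on fixed counts: stop at 2 or fewer responses in 9, reject the null at 10 or more in 24. No cut-offs are given for any other denominator. One patient's status can therefore decide whether the trial continues or is called positive. Leaving the choice until a case arises means making it in a single-arm trial where responses are already known to the team that confirms eligibility.

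**Working it through.** **Inputs, all from section 13.1.** Null rate 0.25, alternative 0.50, one-sided. Stage 1 has 9 patients, continuing with 3 or more responses. Stage 2 adds 15, for 24 in total. Reject with 10 or more responses. Stated type I error 0.05 and power 0.80. The number of treated patients later found ineligible is not given, so 0 to 2 is assumed below.

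**Step 1: reproduce the stated design.** With X the stage 1 responses, binomial (9, p), and Y the stage 2 responses, binomial (15, p):

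P(reject) = sum over x = 3 to 9 of P(X = x) × P(Y ≥ 10 − x)

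- At p = 0.25, the terms for x = 3 to 6 are 0.2336 × 0.0566, 0.1168 × 0.1484, 0.0389 × 0.3135 and 0.0087 × 0.5387. With the small terms for x = 7 to 9, the sum is 0.0485.
- At p = 0.50, the same sum is 0.805.

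The plan's 0.05 and 0.80 reproduce. The problem is the analysis set, not the arithmetic of the design.

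**Step 2: apply both definitions to one boundary case.**
- Final analysis: 24 treated, 10 responders, one responder later found ineligible. Enrolled-and-treated set: 10/24 = 41.7% (exact 95% CI 22.1 to 63.4), which reaches 10 and rejects. Eligible-with-baseline set: 9/23 = 39.1% (19.7 to 61.5), which does not reach 10.
- Stage 1: 9 treated, 3 responders, one of them ineligible. The first set has 3/9 and continues. The second has 2/8 and, with the cut-off unchanged, stops.

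**Step 3: exclude without replacement, regardless of outcome.** Same formula, cut-offs held at 3 and 10:

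| Patients counted | Type I error | Power |
|---|---|---|
| 9 then 24 (none excluded) | 0.0485 | 0.805 |
| 9 then 23 (one stage 2 patient excluded) | 0.037 | 0.766 |
| 9 then 22 (two stage 2 patients excluded) | 0.028 | 0.715 |
| 8 then 23 (one stage 1 patient excluded) | 0.034 | 0.733 |

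**Step 4: exclude only non-responders, without replacement.** The number of responses does not change, so neither decision changes and the type I error stays at 0.0485. Only the reported percentage moves: 9/24 = 37.5% becomes 9/23 = 39.1%.

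**Step 5: exclude only non-responders and replace each with a new patient (hypothetical).** If k non-responders in a stage of n patients are replaced, the stage count becomes X plus a binomial draw on min(k, n − X) new patients at 0.25. The probability of rejecting at a true rate of 25% is then:
- one in stage 1: 0.066 (the chance of continuing rises from 0.40 to 0.47)
- one in each stage: 0.082
- two in each stage: 0.126

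This case needs two things that the protocol does not provide: re-judgment confined to non-responders, and replacement of treated patients.

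**The case against.** The strongest defence is that the sentences can be read together. Eligibility is confirmed at registration and the baseline assessment is mandatory before treatment, so an enrolled patient is an eligible patient with a baseline, and the second sentence only stresses that any duration of therapy suffices. Several eligibility judgments are also prospective (estimated life expectancy, expected compliance) and are not falsified by a later outcome. The protocol describes no re-adjudication after treatment, and the monitoring team includes the statistician and reports to the DSMC. All of this stands as a reason to expect few cases. It does not resolve a case that occurs: the text never equates enrolled with eligible, and the reading fails for a patient found ineligible after treatment.

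A reader might go further and infer that the eligibility clause lets the team drop and replace non-responders, so that the 0.05 error rate holds only if nobody can be dropped. The documents do not support that. Apart from the interruption rule in section 6.1, taken up under the fix, sections 13.1 and 14.6 remove only patients who never start therapy, and no rule replaces a treated patient. Without replacement, dropping non-responders leaves the error rate unchanged (step 4), and exclusion unrelated to outcome lowers it (step 3). The figures of 0.066 to 0.126 belong only to the hypothetical in step 5.

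**Conclusion.** The contradiction is in the current text and should be removed. Its practical size is moderate and conditional. It needs at least one treated patient who is later found ineligible or has no baseline assessment, and the documents give no basis for estimating how many there will be.

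If one occurs, the two definitions can give opposite decisions at the boundary. Under the narrower definition with unchanged cut-offs, the likelier cost is lost power: about 4 points for one stage 2 exclusion (0.805 − 0.766 = 0.039) and about 7 for one stage 1 exclusion (0.805 − 0.733 = 0.072). A type I error above the stated level is not a consequence of the plan as written.

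**What to change.** Make the enrolled-and-treated definition, which the protocol itself calls its primary outcome, the single analysis set for both the stage 1 decision (9) and the final decision (24). In section 13.1:
- Delete the conditions on eligibility and baseline assessment from the evaluability sentence.
- State that treated patients are not replaced.
- State that a treated patient whose response cannot be assessed counts as a non-responder. This is one convention among several, but it does not favour the treatment and keeps the denominators at 9 and 24.
- List ineligibility discovered after treatment as a protocol deviation, and report the rate in eligible patients as a sensitivity analysis.

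Reconcile section 6.1 with the same definition. It makes a patient with an interruption of 6 weeks or more in the first 12 weeks unevaluable for response unless improvement is documented, whereas both sentences in 13.1 accept treatment of any length.

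The change is to wording only. It fixes the denominator by receipt of treatment, before any response is seen, and matches the counts behind the stated error rates. The cost is that the reported rate may be slightly lower if a patient who would have been excluded did not respond.
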